**Notes**

The following questions ask about a variety of different resources that people may use to manage their illness. For each question, please tell me if the item applies to you not at all, a little, a moderate amount, quite a bit, or a great deal.

	Not at all	Little	Moderate amount	Quite a bit	Great Deal	
138. Over the past 6 months, to what extent has your doctor involved you as an equal partner in making decisions about diabetes management strategies and goals? Not at all, a little, a moderate amount, quite a bit, or a great deal?	N	L	M	Q	G	DK NA Ref
139. Over the past 6 months, to what extent has your doctor or other health care advisor listened carefully to what you had to say about your diabetes? Not at all, a little, a moderate amount, quite a bit, or a great deal?	N	L	M	Q	G	DK NA Ref
140. Over the past 6 months, to what extent has your doctor or other health care provider thoroughly explained the results of tests you had done (e.g. cholesterol, blood pressure or other laboratory tests)? Not at all, a little, a moderate amount, quite a bit, or a great deal?	N	L	M	Q	G	DK NA Ref
141. Over the past 6 months, to what extent have you had a flexible work schedule that you could adjust to meet your needs?	N	L	M	Q	G	DK NA Ref
142. Over the past 6 months, to what extent has your workplace had rules or policies that made it easier for you to manage your illness (such as no smoking rules or time off work to exercise)?	N	L	M	Q	G	DK NA Ref
143. Over the past 6 months, to what extent have you had control over your job in terms of making decisions and setting priorities?	N	L	M	Q	G	DK NA Ref
	Not at all	Little	Moderate amount	Quite a bit	Great Deal	

Great. Now I will ask you about your health care.

144.	Do you have any kind of health care coverage, including health insurance, prepaid plans such as HMOs, government plans such as Medicare, or Indian Health Service?	Yes	No	DK NA Ref
145.	Do you have one person you think of as your personal doctor or health care provider? If "No," ask: "Is there more than one, or is there no person who you think of as your personal doctor or health care provider?"	 Yes, only 1  Yes, more than 1  No	DK NA Ref	
146.	Was there a time in the past 6 months when you needed to see a doctor but could not because of cost?	Yes	No	DK NA Ref

147.	About how long has it been since you last visited a doctor for a routine checkup? A routine checkup is a general physical exam, not an exam for a specific injury, illness, or condition.	 Within the past 1-3 months  Within the past 4-6 months  Within the past 7-9 months  Within the past 10-12 months	DK NA Ref
------	---	--	-----------------

The next questions are about the area where you live and travel. Your responses will help explain how easy or difficult it is for you to access health care services.

What is the distance (in miles) that you live from the health care service you would go to for each of the following, and in which town/city is it located:

148.	Routine diabetes care checkups:	City:	Miles:	DK NA Ref
149.	Emergency care:	City:	Miles:	DK NA Ref
150.	Overnight stays in a hospital:	City:	Miles:	DK NA Ref

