### My Peer Advisors Rules

- Be on time!
- Call you regularly during the program.
- Help you learn.
- Listen.

Before every call,  

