S13.	What is your gender? If female: are you pregnant or planning on becoming pregnant in the next 6 months?   Female, pregnant → Thank you so much for your time. You are not eligible for this study since we are looking for people who are not pregnant.  Female, not pregnant → continue to next section  Male → continue to next section
S14.	An important part of enrolling in this study involves completing several data collection visits. Let me tell you a about these data collection visits. 
 
- The first part of this study involves completing an interview over the telephone that will take around 45 to 60 minutes.
 
- During this telephone interview, we will ask you some questions about you and your diabetes.
 
- This call will happen after you decide that you want to participate in the study.
 
- After this phone interview is complete, we will schedule an in-person data collection visit. During this visit, we will measure your blood pressure, weight, and height. Our team will also do a finger stick test to check your “A1c” and “LDL cholesterol” numbers.
 
- The phone interview and in-person visits will be done again after the end of the program.
 
- The in-person data collection visits will be held at a community location. If you are unable to come to a community location, with your permission, a study research assistant will visit you at your home to complete this data collection visit.
 
 Would you be willing to participate in 2 telephone interviews and 2 in-person data collection visits?  No → Thank you so much for your time. You are not eligible for this study since we are looking for people who are willing to participate in telephone interviews and in person data collection visits before and after the program (this is a total of 2 telephone interviews and 2 in person data collection visits.). Have a nice day!  Yes → Continue to next section.

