9. How much support do you get from your health care team for dealing with your diabetes problems? Do you receive...	 A great deal of support  Neutral  No support	 DK  NA  Ref
10. How satisfied are you with the support you get from your health care team for dealing with your diabetes problems? Are you...	 Extremely satisfied  Neutral  Not at all satisfied	 DK  NA  Ref

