### **Purpose of the Research**

---

We are asking you to take part in a research study. This research study will test if Peer Advisors can help patients with diabetes better care for his or her diabetes to improve blood sugar levels, blood pressure, and quality of life. Peer advisors come from the same community as participants and have been trained to help people with diabetes. This study will enroll 500 participants. 250 participants will work with a peer advisor for 6 months and 250 participants in the general education group will receive health education videos. Which program you receive will depend on a random assignment process.

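### At follow-up, the health care advisor named in interview item 139 could be taken to include the Peer Advisor, whom only one arm has

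*Combined protocol and SAP*

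**What the plan says.** Items 138-140 of the Telephone Interview (Appendix E) use a five-point scale from not at all to a great deal, with a six-month recall period. The lead-in is broad: "The following questions ask about a variety of different resources that people may use to manage their illness".

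- Item 138: "has your doctor involved you as an equal partner in making decisions about diabetes management strategies and goals".
- Item 139: "has your doctor or other health care advisor listened carefully to what you had to say about your diabetes".
- Item 140: "has your doctor or other health care provider thoroughly explained the results of tests you had done".

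No interviewer note in this block says whether people from the study are to be counted.

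The Telephone Eligibility Script (Appendix D, S14) says "The phone interview and in-person visits will be done again after the end of the program". The consent text (Purpose of the Research) gives the allocation: "250 participants will work with a peer advisor for 6 months and 250 participants in the general education group will receive health education videos". The same eligibility script puts peer contact at 13-16 calls over six months. In the Activity Book, under My Peer Advisors Rules, the peer's duties include "Call you regularly during the program" and, as a separate bullet, to listen.

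**The concern.** The participant materials attach the word advisor to one role, the Peer Advisor. The recruitment flyer (Appendix D) presents that person as giving individual advice on diabetes care, and the eligibility script says the calls are about diabetes care. Item 139 then asks whether an advisor listened to what the respondent said about diabetes. In the peer arm at follow-up, the peer is a natural candidate for that description. In the video arm there is no such person.

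If some peer-arm respondents include the peer, the same question measures different things in the two arms, and only after randomisation. Balanced baseline groups and adjustment for the baseline score do not remove this, because at baseline nobody has yet had a peer call. At stake is how an arm difference on item 139 is interpreted. A real improvement in the doctor's listening could not be told apart from the peer being counted. The program coaches people on what to say to their doctor (for example, the Client Plan Book pages for calling the doctor), so a gain on this item is one the team might wish to interpret.

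**Working it through.** **1. Who each item asks about**

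| Item | Referent |
|---|---|
| 138 | the doctor |
| 139 | the doctor or another health care *advisor* |
| 140 | the doctor or another health care *provider* |

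Item 145, later in the interview, also uses *provider*. Within the 138-140 block, *advisor* occurs once.

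**2. How far the recall period overlaps the peer calls**

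The In-person Data Collection Form says the peer first calls 1-2 weeks after the baseline visit, and that data collection is repeated at 6 months. The Activity Book schedule lists 11 sessions and 2 check-ins, 11 + 2 = 13 calls, with the last session at week 24. At that session the participant is told that study staff will be in touch within a month. Taking six months as about 26 weeks and the interview at week 24 to 28, the recall period starts no later than about week 28 - 26 = 2. It therefore covers all but the first session or so. The overlap is large but not complete.

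**3. Illustration of size**

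The only stated figure is the allocation, 250 + 250 = 500, which agrees with the total in the Biometric Protocol. The documents give no SD for the item, no share who would count the peer and no dropout rate, so everything else here is assumed:

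- f = share of the peer arm who answer one category higher because they count the peer; 10%, 20% or 30%
- SD of the item, scored 1-5, equal in both arms; 1.0 to 1.4
- no true difference in the doctor's listening; two-sided test at 0.05

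Shift in the arm difference = f × 1 point. SE = SD × √(2/n). Chance of a significant result favouring the peer arm = P(Z > 1.96 - f/SE).

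With n = 250 per arm, SE = 1.0 × √(2/250) = 0.089 and 1.4 × √(2/250) = 0.125. With n = 200 (250 × 0.8, an assumed 20% loss), SE = 0.100 and 0.140.

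| f | f/SE, n = 250 (SD 1.0; 1.4) | Chance, n = 250 (SD 1.0; 1.4) | Chance, n = 200 (SD 1.0; 1.4) |
|---|---|---|---|
| 0.1 | 1.12; 0.80 | 20%; 12% | 17%; 11% |
| 0.2 | 2.24; 1.60 | 61%; 36% | 52%; 30% |
| 0.3 | 3.35; 2.40 | 92%; 67% | 85%; 57% |

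With f = 0 the chance in this direction is the nominal 2.5%.

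**The case against.** The strongest reply is that the form supplied is headed as the baseline interview. Peer calls begin only after the baseline visit, so a baseline form has no peer to exclude, and its silence proves nothing about follow-up. The follow-up form is not shown and may already deal with this. That stands: reuse of the wording is an inference from the eligibility script, and the point is conditional on it.

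It is also fair that misreading is possible but not demonstrated. The item names the doctor first, and the materials present the peer as a community member distinct from doctors, nurses and pharmacists. The share f is therefore unknown and could be near zero. Anyone already answering at the top of the scale cannot move up, so f must be read as the share who actually do.

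Several stronger readings are tempting and are not supported:

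- A reader might infer that peers are paid to listen. The part of the document available (part 2 of 2) describes trained people from the same community and does not mention payment.
- A reader might extend the point to items 9-10, which ask, for example, "How much support do you get from your health care team for dealing with your diabetes problems". Those items do not use the word advisor, have no six-month window, and follow separate questions on family and friends.
- A reader might treat items 138-140 as a doctor-communication scale and compute a bias for its mean. No such scoring is shown, and the SD of a three-item mean is not that of a single item.
- A reader might take the recall period to match the program exactly. By the dates above, it does not.

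**Conclusion.** The point holds in a limited form. If item 139 is reused unchanged at follow-up, its wording can refer to different people by arm, and an arm difference on it could not be attributed to the doctor or clinic. The size cannot be derived from the documents. The illustrative 12-92% rests on 250 analysed per arm, SD 1.0-1.4, and 10-30% of the peer arm rating one point higher; it describes sensitivity and is not a forecast.

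The ambiguity is confined to this one self-report item. A reader might infer that the trial's conclusions are at risk, but the documents do not support that. The Biometric Protocol names HbA1c, blood pressure, weight and physical function as targets, and the consent text names blood sugar, blood pressure and quality of life. The part available gives item 139 no scoring or endpoint role, and A1c, blood pressure, LDL and weight do not depend on it. The change is still worth making because it removes a differential measurement that analysis cannot remove afterwards, at almost no cost.

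**What to change.** In the follow-up interview, in both arms, read one line before items 138-140, such as: *Please think only of your own doctors, nurses and clinic, not anyone from the Living Well study.* Naming the study avoids asking video-arm participants about a peer they never had. Preferably also replace *advisor* with *provider* in item 139, to match item 140. If the follow-up form already does this, nothing more is needed.

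The cost is one spoken sentence and one changed word. The small downside is that item 139 then differs by a word from baselines already taken, identically in both arms, so the between-arm comparison is not harmed.

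If follow-up data have already been collected with the present wording, report item 139 separately and do not interpret an arm difference on it as better communication by the doctor.

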**Notes**

For each of the following questions, please tell me on how good you are at doing the following things.		
151. How good are you at working with fractions? Are you not good at all, a little good, somewhat good, very good, or extremely good?	 Not good at all  A little good  Somewhat good  Very good  Extremely good	DK Ref
152. How good are you at working with percentages? Are you not good at all, a little good, somewhat good, very good, or extremely good?	 Not good at all  A little good  Somewhat good  Very good  Extremely good	DK Ref
153. How good are you at calculating a 15% tip? Are you not good at all, a little good, somewhat good, very good, or extremely good?	 Not good at all  A little good  Somewhat good  Very good  Extremely good	DK Ref
154. How good are you at figuring out how much a shirt will cost if it is 25% off? Are you not good at all, a little good, somewhat good, very good, or extremely good?	 Not good at all  A little good  Somewhat good  Very good  Extremely good	DK Ref
155. When reading the newspaper, how helpful do you find tables and graphs that are parts of a story? Do you find tables and graphs helpful never, rarely, sometimes, often, or very often?	 Never  Rarely  Sometimes  Often  Very often	DK Ref
156. When people tell you the chance of something happening, do you prefer that they use words ("it rarely happens") or numbers ("there's a 1% chance")? Do you always prefer words, usually prefer words, have no preference, usually prefer numbers, or always prefer numbers?	 Always prefer words  Usually prefer words  No preference  Usually prefer numbers  Always prefer numbers	DK Ref
157. When you hear a weather forecast, do you prefer predictions using percentages (e.g., "there will be a 20% chance of rain today") or predictions using only words (e.g., "there is a small chance of rain today")? Do you always prefer percentages, usually prefer percentages, have no preference, usually prefer words, or always prefer words?	 Always prefer percentages  Usually prefer percentages  No preference  Usually prefer words  Always prefer words	DK Ref
158. How often do you find numerical information to be useful? Do you find numerical information useful never, rarely, sometimes, often, or very often?	 Never  Rarely  Sometimes  Often  Very often	DK Ref

	Strongly disagree	Disagree	Neutral	Agree	Strongly agree	
159. Doctors who do medical research only care about what is best for each patient. Do you strongly disagree, disagree, are neutral, agree, or strongly agree?	SD	D	N	A	SA	DK Ref
160. Doctors tell their patients everything they need to know about being in a research study. Do you strongly disagree, disagree, are neutral, agree, or strongly agree?	SD	D	N	A	SA	DK Ref
161. Medical researchers treat people like "guinea pigs". Do you strongly disagree, disagree, are neutral, agree, or strongly agree?	SD	D	N	A	SA	DK Ref
162. I completely trust doctors who do medical research. Do you strongly disagree, disagree, are neutral, agree, or strongly agree?	SD	D	N	A	SA	DK Ref
	Strongly disagree	Disagree	Neutral	Agree	Strongly agree	

**Notes**

The next questions are about your diabetes.				
163.	How old were you when you first found out you had diabetes?	Age:	Year (if needed)	DK NA Ref
164.	How old were you when you were first told you needed to take medications for your diabetes or sugar?	Age:	Year (if needed)	DK NA Ref
165.	Do you take insulin?		Yes          No	DK NA Ref

Now I would like to ask you some questions about general health conditions. Has a doctor, nurse, or other health professional EVER told you that you had any of the following? For each, tell me "Yes," "No," or you're "Not sure."				
166.	Has a doctor, nurse, or other health professional EVER told you that you had a heart attack?		Yes          No	DK NA Ref
167.	Has a doctor, nurse, or other health professional EVER told you that you had angina or coronary heart disease?		Yes          No	DK NA Ref
168.	Has a doctor, nurse, or other health professional EVER told you that you had a stroke?		Yes          No	DK NA Ref
169.	Has a doctor, nurse, or other health professional EVER told you that you had some form of arthritis, rheumatoid arthritis, gout, lupus, or fibromyalgia?  INTERVIEWER NOTE: Arthritis diagnoses include: 
 
• rheumatism, polymyalgia rheumatica
 
• osteoarthritis (not osteoporosis)
 
• tendonitis, bursitis, bunion, tennis elbow
 
• carpal tunnel syndrome, tarsal tunnel syndrome
 
• joint infection, Reiter's syndrome
 
• ankylosing spondylitis; spondylosis
 
• rotator cuff syndrome
 
• connective tissue disease, scleroderma, polymyositis, Raynaud's syndrome
 
• vasculitis (giant cell arteritis, Henoch-Schonlein purpura, Wegener's granulomatosis, polyarteritis nodosa)
 
		Yes          No	DK NA Ref
170.	Has a doctor, nurse, or other health professional EVER told you that you had a depressive disorder, including depression, major depression, dysthymia, or minor depression?		Yes          No	DK NA Ref
171.	Has a doctor, nurse, or other health professional EVER told you that you had kidney disease? Do NOT include kidney stones, bladder infection or incontinence.  INTERVIEWER NOTE: Incontinence is not being able to control urine flow.		Yes          No	DK NA Ref

The next question asks about difficulties in thinking or remembering that can make a big difference in everyday activities. This does not refer to occasionally forgetting your keys or the name of someone you recently met. This refers to things like confusion or memory loss that are happening more often or getting worse. We want to know how these difficulties impact you.				
172.	During the past 12 months, have you experienced confusion or memory loss that is happening more often or is getting worse?		Yes          No	DK NA Ref

**Notes**

Thank you for hanging in there. Next, I have few more questions about your background.

173. Do you have a doctor that you see regularly for you diabetes care? [CLEARLY PRINT]	 Yes	 No
---	------------------------------	-----------------------------

First:
Last:
City:

174. Are you of a Hispanic, Latino/a, or Spanish origin?  (Read if necessary: Puerto Rican, Cuban/Cuban American, Dominican (Republic), Mexican, Mexican American, Central or South American, Other Latin American, Other Hispanic/Latino)	 Yes  No	DK Ref
--	---	-----------

175. What race or races do you consider yourself to be? (Select all that applies)	 White  Black / African American  American Indian	 Asian or Pacific Islander  other, specify: _____	DK Ref
--	---	--	-----------

176. How old are you?	Age today in years:	DK Ref
-----------------------	----------------------------	-----------

177. Are you married, divorced, widowed, separated, never married, or living with a partner?	 Married  Divorced  Widowed	 Separated  Never married  Living with a partner	DK Ref
--	---	--	-----------

178. Are you currently employed for wages, self-employed, out of work for 1 year or more, out of work for less than 1 year, homemaker, a student, retired, unable to work. (select all that applies)	 Employed for wages  Self-employed  Out of work for 1 year or more  Out of work for less than 1 year	 Homemaker  A student  Retired  Unable to work	DK Ref
---	---	---	-----------

179. Is your annual household income from all sources?	 Less than \$10,000  \$10,000 to less than \$20,000  \$20,000 to less than \$30,000  \$30,000 to less than \$40,000  \$40,000 to less than \$50,000  \$50,000 to less than \$60,000  \$60,000 to less than \$70,000  \$70,000 to less than \$80,000  \$80,000 to less than \$90,000  \$90,000 to less than \$100,000  \$100,000 or greater	 don't know  refused
--	--	---

**Notes**

180. What is the HIGHEST level of school completed or the highest degrees received?	 Never attended or only attended kindergarten  Grades 1 through 8 (elementary)  Grade 9 through 11 (elementary)  Grade 12 or GED (High school graduate)  College 1 year to 3 years (Some college or technical school)  College 4 years or more (College graduate)
	 don't know  refused

181. How often do you use text messaging?	 Never  Rarely  Frequently  All the time	 DK  Ref
182. How often do you use the internet?  [Prompt if needed] Go online.	 Never  Rarely  Frequently  All the time	 DK  Ref
183. Where do you most often use the internet?	 At home  A friend or family member's home  Library  On a cell phone  Other ( specify ): _____	 DK  Ref

184. Indicate sex of respondent. Ask only if necessary	 Male  Female
---	--

**Notes**

F1. We are now finished with the interview. Thank you so much for taking time today to answer these questions. The next step is to schedule an in-person data collection. As we mentioned before, during this visit, Living Well Program research assistants will measure your blood pressure, blood sugar, cholesterol, weight, and height.

- Wearing a loose fitting shirt is recommended to the in-person data collection visit so that we are able to measure your blood pressure.
- We ask that you not to drink any caffeine (from coffee, tea, or soda), eat, do any heavy physical activity, smoke, or ingest alcohol for 30 minutes prior to the in person data collection visit.

There are 2 options for this visit, which will last from 45-60 minutes. Option 1 is Living Well research assistants to come to your home to do the measurements. Option 2 is for you to meet us a data collection visit that is scheduled at a community venue in your community.

Are you interested in the in-home data collection or would you like to meet us for a group data collection day?

In home data collection preferred: (schedule date / time / location & directions)

Group data collection at community venue preferred: (schedule for a data collection)

The next data collections in your area are scheduled for \_\_\_\_\_(DATE / TIME) at \_\_\_\_\_(LOCATION).

Which dates/times are convenient for you? [Schedule data collection] \_\_\_\_\_

F2. [Scheduled data collection] Great! I have your data collection date scheduled for [date / time / location].

You will receive a reminder card in the mail at this address 5 -7 days before this date. You will also receive a telephone call to remind you of the date the day before the visit.

F3. Verify telephone / contact information:

F4. Verify location / directions:

F5 Great! I have your data collection date scheduled for [date / time / location]. A research study assistant will meet you at (\_\_\_\_\_ location) and at (\_\_\_\_\_ time/date).

Thank you so much! Have a great day.

